10.4 Force markers

10.4.1 Dynamometer

The dynamometer is an instrument used to measure muscle strength objectively. In this study will be used the static dynamometer that demonstrated measurement reliability in other clinical trials (HIRANO et al., 2020; MARTINS et al., 2018).

10.4.2 Jump tests

The jump tests are used as a measure of explosive strength and muscle power and this methodology will also be used in this research. The effectiveness of strength assessment

in the countermovement jump test has already been validated in other clinical studies (CARBAKAPA et al., 2023).

10.4.3 Functional tests

Functional tests assess strength in more complex movements related to day-to-day activities. In these studies, the 6-minute step test will be applied, as determined its reliability for the evaluation of muscle strength in a previous study (ARCURI et al., 2016).

10.4.4 Muscular endurance test

Muscle endurance tests assess the ability of muscles to sustain a contraction for a prolonged period. In this study will be used the abdominal resistance test, through the plank test, already reproduced effectively in another study (KOUMANTAKIS et al., 2021).

10.5 Aminogram

A sample of 250 ml of juçara juice will be sent to the laboratory C.B.O. laboratory analyzes Ltda, for analysis of Total Amino Acids: Aspartic Acid, Glutamic Acid, Alanine, Arginine, Cystine, Phenylalanine, Glycine, Hydroxyproline, Histidine, Isoleucine, Leucine, Lysine, Methionine, Proline, Serine, Taurine, Tyrosine, Threonine, Valine, Tryptophan and Total Proteins. Of all these amino acids the ones that are essential and the body does not produce, will be those that will make the difference compared to other foods in age-induced bone loss (ZIQUAN et al, 2022).

10.6 Subjective analysis of fatigue

A questionnaire will be developed about the subjective perception of patients about the effects of the treatment employed in the recovery of muscle fatigue. The questions will be based on the Chalder scale and the International Short-Form Physical Activity Questionnaire (IPAQ-SF) (LEE et al., 2011). However, the feeling of improvement or not of physical fatigue after exercise will be the focus of the preparation of a new and unprecedented questionnaire

11. Statistical analysis

The results will be expressed as mean \pm SEM (standard error of the mean). Statistical analysis will be performed by one-way analysis of variance (ANOVA) (repeated measures), followed by Tukey's post hoc test, using the Prism software (Prism 6.0, GraphPad Software, Inc., San Diego, CA, USA). The differences will be considered significant when $p < 0.05$.

REFERENCES

ARCURI, J. F. et al. Validity and Reliability of the 6-Minute Step Test in Healthy Individuals: A Cross-sectional Study. **Clinical Journal of Sport Medicine**, v. 26, n. 1, p. 69-75, Jan. 2016.

BUTCHER, J. T. et al. Effect of myostatin deletion on cardiac and microvascular function. **Physiological Reports**, v. 5, n. 23, e13525, Dec. 2017.

CABARKAPA, D. et al. Position-specific differences in countermovement vertical jump force-time metrics in professional male basketball players. **Front Sports Act Living**, v. 20, n. 5, p. 1218234, Jul. 2023.

CARDOSO, A.L. et al. An Update on the Biological Activities of *Euterpe edulis* (Juçara). **Planta Médica**, v. 84, n. 8, p. 487-499, may., 2018.

CARROLL, T. J.; TAYLOR, J. L.; GANDEVIA, S. C. Recovery of central and peripheral neuromuscular fatigue after exercise. **Journal of Applied Physiology**, v. 122, n. 5, p. 1068-1076, May. 2017.

ELY, M. R. et al. A single dose of histamine-receptor antagonists before downhill running alters markers of muscle damage and delayed-onset muscle soreness. **Journal of Applied Physiology** v. 122, n. 3, p. 631-641, mar. 2017.

FANG, P. et al. Adipose-Muscle crosstalk in age-related metabolic disorders: The emerging roles of adipo-myokines. **Ageing Research Reviews**, v. 84, p. 101829, Feb. 2023.

FELZENSZWALB, I. et al. Toxicological evaluation of *Euterpe edulis*: a potential superfruit to be considered. **Food and Chemical Toxicology**, v. 58, p. 536-44, Aug. 2013.

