[figure not shown]

Official Title: Effect of supplementation with *Euterpe edulis* on the physical and mental performance of healthy men submitted to physical exercises

Ethical committee Protocol No: 6.202.888

Study protocol

1. Type of study

This is a clinical study, double blind, with the purpose of offering the juice of *E. edulis*, daily for 4 weeks before the day of the final evaluation, compared to the control. There will be about 40 men, aged 19 to 30 years, who perform regular physical exercises, in total of 150 min per week, at a minimum of 3 months.

2. Experimental Protocol

The men will be randomized into two groups, called GJ who will receive the sample and GP who will receive the placebo. The sample consists of 250 mL of juçara juice and the placebo which is 250 mL of water with pectin and natural dye. Research subjects will maintain their exercise routine, as well as fill out a food diary that will be sent electronically. The research will be for 11 days, and on day 1 (D1) of the research he will have the blood collected. On day 11 of the D11 survey, at time zero he will have the blood collected, and then consume the sample or the placebo. Two hours after he will be subjected to the battery of exercises, following 1. Dorsal dynamometer, 2. shoulder dynamometer, 3. manual dynamometer, 4. ergospirometry + electrocardiogram + digital lactate, 5. jump test for 1 min (amounts of jumps), 6. Pollock abdominal test and 7. functional mobility test. At the end, the blood will be collected, and a psychological form will be applied. After 2 and 7 days of physical exercise will be applied visual pain test.

3. The size of the sample

The calculation of the sample of patients for this study was performed using the software G*Power3.1.9.7 (Public domain). Considering the alpha value equal to 0.05 and the power of test $1 - \beta$ as 95% (0.95, that is, determining that the probability of type II error (β) should not be greater than 5%), the value of 20 patients was reached.

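### Section 10.6 plans to measure fatigue with a questionnaire that does not yet exist and asks about perceived treatment effect, so a group difference could not be read as a difference in amount of fatigue

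*Combined protocol and SAP*

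**What the plan says.** Section 10.6 is the only text on the fatigue outcome. It makes four statements.

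- The instrument is still to be written: "A questionnaire will be developed about the subjective perception of patients about the effects of the treatment employed in the recovery of muscle fatigue".
- Its sources are two existing instruments: "The questions will be based on the Chalder scale and the International Short-Form Physical Activity Questionnaire (IPAQ-SF"). The one reference given there is a validity review of the activity questionnaire.
- After the word However, it says that "the feeling of improvement or not of physical fatigue after exercise will be the focus" of a new form.
- That form is described as "the preparation of a new and unprecedented questionnaire".

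On timing, sections 2 and 8 list these self-report items around the D11 exercise: "At the end, the blood will be collected, and a psychological form will be applied", and "After 2 and 7 days of physical exercise will be applied visual pain test". Section 2 lists only a blood sample on D1. Neither section mentions the fatigue questionnaire.

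On blinding, section 1 states "This is a clinical study, double blind". Sections 2 and 9 describe the placebo as water with pectin and a dye. Section 11 gives one general analysis for all results and nothing specific to the questionnaire.

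**The concern.** Three features make the result hard to read as fatigue.

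1. **What is asked.** A question "about the effects of the treatment employed in the recovery of muscle fatigue" calls for an opinion about the product. A feeling of improvement or not is a judgement of change. Neither records how fatigued the man is.
2. **Exposure to guessing.** A man who believes he had the juice may credit it with an effect, and one who believes he had placebo may not. A question that names the treatment invites this more directly than a question about present fatigue.
3. **No defined measurement.** Without scoring, a baseline and fixed times, it is not settled what number would be compared between groups, or when.

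At stake is the trial's only planned self-report of fatigue. A positive result could reflect belief about the drink, and a null result could reflect an insensitive form. A missing D1 reading cannot be recovered after enrolment.

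**Working it through.** The main question is one of measurement, so the first three steps set the text side by side. The fourth shows what arithmetic can and cannot add.

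**Step 1. The plan's own standard for other measures.**

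| Measure | Support given in the plan |
|---|---|
| Dynamometer (10.4.1) | Reliability in other trials, two citations |
| Jump test (10.4.2) | Validation statement, one citation |
| Six-minute step test (10.4.3) | Reliability statement, one citation |
| Plank test (10.4.4) | Prior use, one citation |
| Fatigue questionnaire (10.6) | To be developed; the only citation concerns the activity questionnaire |

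Fatigue falls short of the standard that the plan applies to every strength and endurance test.

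**Step 2. Timing.** There are two possible readings of the psychological form given at the end of D11. If it is the section 10.6 questionnaire, it is completed once, at the end of exercise, with no baseline and no reading during recovery. If it is a different form, the fatigue questionnaire has no administration time at all. The text does not say which. On either reading there is no D1 value and no follow-up value.

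**Step 3. Blinding.** The placebo's dye addresses colour. Section 9 characterises the juice by its phenolics, anthocyanins, protein and lipid. No flavour matching is described, and no question asks men which drink they think they had. Guessing is therefore possible and would go undetected. The documents do not show that it will happen.

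**Step 4. Effect of random error on power (illustration only).**

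*Plan's figure.* Section 3 gives 20 patients at alpha 0.05 and power 95%, with no endpoint, effect size, SD or test, so it cannot be reproduced. Working backwards with a two-sided two-sample t-test, it implies d = 1.17 if 20 is per arm (about 40 men) and d = 1.71 if 20 is the total.

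*Assumptions.* 20 per arm with 1:1 allocation, two-sided alpha 0.05, true effect d, reliability r.

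*Formulas.* Observed effect = d × √r. Power comes from the noncentral t with 38 degrees of freedom and noncentrality (d × √r) × √(20/2). For example, d = 0.8 and r = 0.5 give 0.8 × 0.707 = 0.566, noncentrality 0.566 × 3.162 = 1.79, and power 41%.

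| Assumed true d | r = 1.0 | r = 0.9 | r = 0.8 | r = 0.7 | r = 0.5 |
|---|---|---|---|---|---|
| 0.5 | 34% | 31% | 28% | 25% | 19% |
| 0.8 | 69% | 65% | 60% | 54% | 41% |
| 1.17 | 95% | 93% | 90% | 86% | 72% |

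Every d and r here is an assumption; only 1.17 is derived from a figure in the plan. The table covers random error alone. It does not represent expectation bias or a form that measures something other than fatigue, and more men would cure neither.

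**The case against.** The strongest reply is that the trial is randomised and double blind, with a coloured, pectin-containing placebo. If blinding holds, a difference between groups is still a valid test of no effect on whatever the form records. This stands. It rules out saying that the result has no interpretation; what is lost is its interpretation as an amount of fatigue.

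Three stronger readings are tempting, and the documents do not support them.

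- **That the total will mix fatigue and activity.** Section 10.6 mentions no total and no scoring. Being based on two instruments does not mean that their items are summed, and the sentence opening with However leaves open whether one form or two are meant.
- **That fatigue is measured at the wrong time, before recovery.** This equates the psychological form with the fatigue questionnaire. Nothing links them. The supportable statement is that no time is given.
- **That power falls by a known amount.** A fall from 69% to between 41% and 60% requires an assumed 0.8 SD effect, an assumed reliability of 0.5 to 0.8, and an error-free comparator that no existing scale would match. At d = 0.8, the gap between reliabilities of 0.9 and 0.8 is 65% against 60%.

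It can also be said that the plan does not show the named fatigue scale to suit fatigue after exercise in healthy men. That is correct, and the fix is conditional for this reason.

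**Conclusion.** The concern holds in a limited form. Section 10.6 commits the fatigue outcome to an undeveloped questionnaire worded around treatment effect and improvement, with no scoring, time, baseline or validation step. Followed as written, it yields a judgement about the product, and a group difference could not be read as a difference in amount of fatigue. The exposure to expectation bias is conditional on men guessing their drink, which the plan neither checks for nor rules out by flavour matching.

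The size is not known. The direction of the power effect is certain (less reliability, less power), but its amount depends on figures that the plan does not give.

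The plan names no primary outcome, so fatigue cannot be ranked. The strength, psychomotor and blood outcomes are untouched. This should be changed before enrolment, but it does not undermine the trial as a whole.

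**What to change.** Rewrite section 10.6 and add the questionnaire to the schedule in sections 2 and 8.

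1. Define the fatigue outcome as the level of current fatigue, asked identically in both groups with no mention of the treatment.
2. Use an existing fatigue scale with its own scoring. The scale already named is the natural candidate if its recall period suits the time points below; the sponsor should check this first.
3. Give it at D1, on D11 before exercise and at the end of exercise, and with the pain test 2 and 7 days after. A D11 reading alone is not a baseline, because the men will by then have taken the product for 10 days.
4. Compare groups with adjustment for the D1 value, and name in advance the time point that carries the comparison.
5. Keep the IPAQ-SF separate, given once at D1, as a descriptor or covariate.
6. Keep the perceived-improvement items as exploratory, and state whether the psychological form is a different instrument.

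These times follow the 11-day schedule in sections 2, 8 and 9. Section 1 speaks of 4 weeks, and the two must be reconciled before the times are fixed.

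The cost is one rewritten section and a few minutes at contacts already planned. The downside is slightly longer forms, and the new questionnaire loses its main role.

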On day 11 of the D11 survey, at time zero he will have the blood collected, and then consume the sample or the placebo. Two hours after he will be subjected to the battery of exercises, following 1. Dorsal dynamometer, 2. shoulder dynamometer, 3. manual dynamometer, 4. ergospirometry + electrocardiogram + digital lactate, 5. jump test for 1 min (amounts of jumps), 6. Pollock abdominal test and 7. functional mobility test. At the end, the blood will be collected, and a psychological form will be applied. After 2 and 7 days of physical exercise will be applied visual pain test.

9. Preparation of Juçara juice

The preparation will be obtained with the same methods already well established in previous studies (SCHULZ et al., 2016.; MENDES et al., 2021). Participants will receive 250 ml of water + purple dye + pectin (control) or commercial samples of juçara (*E.edulis*) refrigerated to 4°C to 10°C, per day, for 10 days, and on the 11th will be the exercise and on this day will be administered the juice of the juçara 2 h before on the day of the monitored exercise. The chemical characterization of *Euterpe edulis* will be with at least 350.0 + or - 17.5 mg of total phenolics (gallic acid equivalent), 186.0 + or - 7.5 mg of total monomeric anthocyanins (cyanidin 3-glycoside), 0.73 + or less 0.01 g of proteins, and 2.75 + or - 0.03 g of lipids (ether extract). During the 10 days of previous treatment, maintain the routine of physical exercises.

10. Values evaluated

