10.3 Collection of blood samples and analysis of biomarkers

In the blood collection will be collected samples of 8 ml of the cubital vein of the forearm of the patients according to the method used in Mendes et al. (2021). The samples will be stored in tubes containing ethylenediamine tetraacetic acid (EDTA) 10 or without anticoagulants. The serum should be acquired by the centrifugation method (1000 x g for 10 minutes at 4°C) and stored at – 80°C in polypropylene microcentrifuge tubes until analysis.

Pro-inflammatory biomarkers will contain acute phase proteins such as the cytokines TNF-alpha, IL-6, IL-1 beta, monocyte chemoattractant protein 1, and adhesion molecules. Anti-inflammatory markers: cytokines such as IL-10 and adiponectin that acts on muscles as anti-inflammatory cytokines (FANG et al., 2023).

The serum levels of the biomarkers will be determined by cytometry (flow cytometer FACSverse, BD Biosciences), using a commercial kit Cytometric Bead Array Human Inflammation kit, according to the manufacturer's instructions. Data will be analyzed using FCAP arrayTM (MENDES et al., 2021; SCHULZ et al., 2016)

Blood samples will be collected 1 hour before the high-intensity strength exercise, in the condition of muscle rest. From that moment the participants, randomly divided into two groups, will be selected to drink the extract of juçara (*Euterpe edulis*) or the placebo. New blood samples will be collected after the completion of the muscular effort, specifically 3 minutes after the exercise performed, in addition to the 3rd sample after 24 hours of rest.

Will be evaluated in the blood samples collected: plasma biomarkers, which include lactate concentration (LA). In plasma, creatine kinase (CK), total antioxidant capacity (TAC) and concentrations of testosterone (T), cortisol © and growth hormone (GH) will be analyzed. In addition to serum concentrations of inflammatory biomarkers such as interleukins (IL-6, IL-8, IL10) and TNF-alpha.

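### Section 11 specifies a one-way repeated-measures ANOVA with Tukey, which contains no proper juice-placebo comparison for two parallel groups of different men

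*Combined protocol and SAP*

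**What the plan says.** Section 2 sets up a parallel design: "The men will be randomized into two groups, called GJ who will receive the sample and GP who will receive the placebo". Sections 3 and 7 repeat the two-group split, and section 1 gives the purpose as comparing juice with control. No crossover is planned; the term occurs only in titles in the reference list.

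Section 11 is the whole analysis plan. It gives mean ± SEM, then "Statistical analysis will be performed by one-way analysis of variance (ANOVA) (repeated measures"), Tukey's post hoc test, Prism 6.0 and a 0.05 threshold. It does not name the factor, the contrasts, a baseline or a main time point.

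Measurement times, which decide what can be analysed as repeated, are as follows.

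- **Blood, section 2:** "on day 1 (D1) of the research he will have the blood collected", then day 11 before the drink and day 11 after exercise.
- **Blood, section 10.3:** "Blood samples will be collected 1 hour before the high-intensity strength exercise, in the condition of muscle rest", then 3 minutes after exercise, "in addition to the 3rd sample after 24 hours of rest". On drinking it says "From that moment the participants, randomly divided into two groups, will be selected to drink the extract".
- **Intake:** section 9 has "per day, for 10 days, and on the 11th will be the exercise", while section 1 has "daily for 4 weeks before the day of the final evaluation".
- **Exercise battery:** sections 2 and 8 list it on day 11 only. Sections 3 and 7 add that each man is assessed at the start and at the end of the exercise, without naming an outcome.
- **Pain:** 2 and 7 days after exercise.
- **Psychomotor tests (10.1, 10.2) and fatigue questionnaire (10.6):** no clear time is given.

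**The concern.** A one-way repeated-measures ANOVA has one within-subject factor. It compares several measurements on the same men. Juice and placebo are given to different men, so treatment cannot be that factor. The trial's main question therefore has no stated test. An analyst who follows section 11 literally must either omit the treatment comparison or enter the data as if each juice man were paired with a placebo man. An analyst who departs from it chooses the test after the data exist, across many biomarkers and performance outcomes.

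**Working it through.** **Inputs.** From the documents: two parallel arms, and 20 men (section 3) or about 40 (section 1), so 10 or 20 per arm if the arms are equal. The 20 cannot be reproduced, because no effect size, SD, endpoint or test is given, so it does not show which test was planned. Assumed, not in the documents: SD 1, equal within-man correlation ρ = 0.5 / 0.7, three samples per man, one pooled error variance, no sphericity correction (section 11 names none), and no missing data. Paired results below are for ρ = 0.5 / 0.7.

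**Reading A: the factor is time.** The model has time and participant terms and no group or group-by-time term. It yields no juice-placebo test. For an outcome with one value per man it is not defined.

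**Reading B: the columns are the 2 × 3 = 6 group-by-time cells, with one GJ man and one GP man sharing each row.**

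*Error variance.* Of the 6 × 5 / 2 = 15 column pairs, 6 are within the same man (3 per arm) and have correlation ρ; the other 9 have correlation 0. The expected residual mean square is 1 − (6/15)ρ = 1 − 0.4ρ = 0.80 / 0.72.

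- A GJ-GP contrast needs 1, so the error is 0.80 / 0.72 of the correct value.
- A within-man contrast needs 1 − ρ = 0.50 / 0.30, so the error is 0.80/0.50 = 1.6 and 0.72/0.30 = 2.4 times the correct value.

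*Overall F.* The five column contrasts have variances 1 − ρ (four times) and 1 + 2ρ (once), so sphericity fails. Box's epsilon is (sum)² / (5 × sum of squares):

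- ρ = 0.5: 4² / (5 × 5) = 0.64
- ρ = 0.7: 3.6² / (5 × 6.12) = 0.42

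A value below 1 means that the uncorrected F rejects too often. Simulation (20,000 trials per scenario) agrees.

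| Row-matched, three samples | 10 per arm | 20 per arm |
|---|---|---|
| Overall F, no effect of any kind | 7.6 / 9.9% | 7.6 / 9.7% |
| Post-exercise GJ-GP Tukey pair, no effect | 1.2 / 2.0% | 1.2 / 1.8% |
| Any same-time GJ-GP pair, no effect | 3.3 / 4.6% | 3.1 / 4.0% |
| Power of post-exercise pair, 1 SD effect | 35 / 41% | 71 / 75% |
| t-test at that time, 0.05 | 56% | 87% |
| t-test at that time, 0.05/3 | 37% | 74% |
| ANCOVA on a pre-intervention sample, 0.05/2 | 53 / 72% | 89 / 98% |
| Two random row orders disagree on that pair, 1 SD effect | 8 / 11% | 6 / 6% |

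If the post-exercise SD is twice the others, the post-exercise Tukey pair rejects in about 6.5-8% of trials with no effect, because the pooled error is then too small for that pair.

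Tukey's 15 pairs compare cell means. The group-by-time effect is a difference of differences, such as (GJ after − GJ before) − (GP after − GP before), and is none of the 15.

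*Outcome measured once (two columns).* The paired form has n − 1 degrees of freedom against 2n − 2 for a two-sample t-test. Type I error is about 5%. Power at 0.8 SD is 35.9% against 39.5% (10 per arm) and 67.0% against 69.3% (20 per arm). Two row orders disagree in 14% and 9% of trials.

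**Reading C: an ordinary one-way ANOVA by group.** This is valid for an outcome measured once. Section 11 does not say it, and its only qualifier is repeated measures.

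**The case against.** The best defence is that the authors loosely meant a mixed group-by-time ANOVA. That may be so, but the text says one-way and names no group term. If that was the intent, the correction is a rewording.

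Second, the start-and-end assessment in sections 3 and 7 could explain the repeated-measures label for the battery. This stands as a possibility. The misfit for the battery is therefore conditional on reconciling those sentences with sections 2 and 8. Two measurements per man would still leave no group term.

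Third, the blood schedules may be compatible. The before and after draws in sections 2 and 10.3 could be the same two, with D1 and 24 hours as additions, giving four samples. The wording in 10.3 on drinking could describe the day-11 portion alone, which would leave D1 as a natural baseline. This also stands. It is a reason to reconcile the sections, and it does not supply a treatment comparison.

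A reader might infer more than the documents support:

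- **That the plan necessarily produces false juice claims.** Same-time Tukey pairs stay below 5% under equal SDs. An F test on time that detects a shared exercise effect is not a false juice-placebo finding. Claims from separate within-arm p-values would be misleading, but the plan states no such rule.
- **That false positives are never inflated.** The overall F and the doubled-SD case contradict this.
- **That power is lost in general.** Against a t-test corrected for three times, the loss is about 2-3 points at ρ 0.5, with none at ρ 0.7. The clear loss is against a baseline-adjusted analysis, and only if a pre-intervention sample exists.

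**Conclusion.** The stated method is wrong for the design and must be changed before analysis. This conclusion follows from the text alone: followed literally, section 11 either has no treatment term or matches unrelated men by row.

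The size depends on the reading. Under the time reading, the juice-placebo comparison is absent. Under the row-matched reading, the overall F rejects in about 7.6 / 10% of null trials, and conclusions on the post-exercise pair differ between row orders in roughly 6-11% of trials with a 1 SD effect. For outcomes measured once, row matching is approximately valid but slightly inefficient and dependent on row order. These figures are illustrative; they rest on the assumed SDs, correlations, effect sizes, three samples and uncorrected sphericity. The need for the change does not depend on them.

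**What to change.** Replace the test in section 11 by outcome.

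1. **Repeated blood markers, and pain at 2 and 7 days:** a mixed model, or a two-way mixed ANOVA, with group, time, group-by-time and a participant effect. Name the time at which the GJ-GP difference is the main estimate. Reconcile the blood schedules and the start and duration of intake across sections 1, 2, 9 and 10.3, then state which sample precedes the intervention (D1 in section 2, if that is confirmed) and adjust the blood markers for it.
2. **Outcomes measured once on day 11:** a two-sample t-test or a linear model on group. If sections 3 and 7 mean two measurements, use item 1.
3. **Psychomotor tests and fatigue questionnaire:** state when they are measured, then use item 1 or item 2 accordingly.
4. **All outcomes:** base any claim of a juice effect on the GJ-GP difference with its 95% CI, not on within-group changes.

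A two-way mixed ANOVA with two-group tests would be enough to close the gap; baseline adjustment is where power is gained. The cost is a rewrite of section 11 once the schedules agree, and slightly more analysis work. No participants are added.

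### Section 11 plans repeated-measures ANOVA with Tukey's test but does not address sphericity; if the ordinary pooled error is used, some time contrasts may get intervals too wide and others too narrow, depending on the marker

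*Combined protocol and SAP*

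**What the plan says.** Section 11 is the whole statistical plan. It names "one-way analysis of variance (ANOVA) (repeated measures), followed by Tukey's post hoc test", run in Prism 6.0 at a 5% significance level. It does not mention sphericity, a test or correction for it, or whether the post hoc comparisons use a pooled or a pair-specific error. It names no group factor and no group-by-time term, although Section 2 randomizes the men to juice or placebo.

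The times to be compared are described in two ways:

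- Section 2 says that "on day 1 (D1) of the research he will have the blood collected". It then gives a D11 draw before the product and another at the end of the exercise battery. Section 8 repeats the D11 part. Neither section has a 24-hour draw.
- Section 10.3 gives a resting draw one hour before exercise. It then says "New blood samples will be collected after the completion of the muscular effort, specifically 3 minutes after the exercise performed", and adds a third draw after 24 hours of rest. It has no D1 draw.

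No SD, variance or between-time correlation is given for any marker at any time.

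**The concern.** Ordinary Tukey comparisons after a repeated-measures ANOVA give every pair of times the same standard error, taken from one residual mean square. That is right only if the difference between any two times varies equally from man to man, whichever two are chosen.

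The draws here are unevenly placed. Two draws on D11 are hours apart, while D1 is 10 days earlier. In Section 10.3 the third draw is a next-day recovery value. The same method must serve lactate, CK, antioxidant capacity, three hormones and several cytokines. It is unlikely that all of them meet the condition over such spacing.

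Where it fails, contrasts that are truly precise get inflated intervals, so real changes can be missed. Contrasts that are truly noisy get intervals that are too short, and the overall F test rejects too often.

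**Working it through.** **Is there a figure to reproduce?** Not on this point. The sample-size section says only that "the value of 20 patients was reached", without effect size, test family, number of measurements or correlation, so that figure cannot be re-derived. It is used here only as the number of men per simulated analysis. The standard-error ratios below do not depend on it.

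**Inputs.** The draw times come from Sections 2, 8 and 10.3. All SDs and correlations are assumptions.

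**Formula.** For times i and j, the variance of the paired difference is V = SDi² + SDj² − 2·r·SDi·SDj. The pooled mean square estimates half the mean of V over all pairs. Hence

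pooled SE ÷ true SE = √(mean V ÷ V of that pair).

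**Case A: Section 2 times** (D1, D11 rest, post-exercise), all SDs 1, correlation 0.9 between the two D11 draws and 0.6 otherwise.

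- D1–rest and D1–post: V = 2(1 − 0.6) = 0.8 each. Rest–post: V = 2(1 − 0.9) = 0.2. Mean = 1.8/3 = 0.6.
- Rest–post ratio: √(0.6/0.2) = 1.73. The variance used is 3 times the true one, roughly as if two thirds of the men had been discarded for that contrast.
- D1–rest and D1–post ratio: √(0.6/0.8) = 0.87, so 13% too small.

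**Case B: Section 10.3 times** (rest, 3 minutes, 24 hours), SDs 1, 1.2, 3, correlation 0.7.

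- Rest–3 min: 1 + 1.44 − 1.68 = 0.76. Rest–24 h: 1 + 9 − 4.2 = 5.80. 3 min–24 h: 1.44 + 9 − 5.04 = 5.40. Mean = 11.96/3 = 3.99.
- Ratios: √(3.99/0.76) = 2.29, √(3.99/5.80) = 0.83, √(3.99/5.40) = 0.86.

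**Case C: as B, with the large SD at 3 minutes** (1, 3, 1.2). The same three variances change places. Rest–24 h now has V = 0.76 and a ratio of 2.29, so its interval is too wide.

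**Case D: Section 2 times with mild differences**, SDs 1, 1, 1.2, correlation 0.7.

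- V = 0.60, 0.76, 0.76; mean 0.707. Ratios: 1.09, 0.96, 0.96. Little is lost.

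**Case E: unequal SDs that do no harm**, SDs 1.18, 1.41, 1.67 with correlations 0.42, 0.56, 0.59.

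- V = 1.98, 1.97, 2.00. All ratios are 1.00.

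**Error rates by simulation** (no true time effect, 20 men, nominal 5%):

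| Case | F-test size | Tukey, per pair |
|---|---|---|
| Spherical control | about 5% | about 2% |
| A | 6.7% to 6.9% across runs | about 4.5% for the 10-day pairs, about 0.01% for rest–post |
| B | about 7.6% | – |
| E | 4.8% (family-wise 4.9%) | about 2% |

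**Limit on the understatement.** With three times, the SD of one difference cannot exceed the sum of the other two. The two smaller variances therefore total at least half the largest. Then mean V is at least (1 + 0.5)/3 = half the largest V, and no ratio can fall below √0.5 = 0.71. A standard error can be at most 29% too small, but there is no matching ceiling on how far it can be too large.

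**The case against.** The strongest reply is that the plan is silent rather than wrong. Section 11 does not say that the post hoc error is pooled, and the behaviour of the named software cannot be settled from the documents. That stands, so the point is conditional on the ordinary form of the test.

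A reader might also infer one of four stronger claims. The documents do not support them.

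- *The variances cannot be equal, so the method must fail.* The condition concerns paired differences, not variances. Case E meets it with unequal SDs and unequal correlations, and no marker's SDs are given.
- *The 24-hour contrasts are always too narrow and the resting ones too wide.* This needs the 24-hour value to be the most variable. Case C reverses the direction for rest versus 24 hours.
- *The 24-hour intervals are far too narrow.* In case B the shortfall is 17%, and with three times it can never exceed 29%.
- *There are four times: D1, D11 rest, 3 minutes and 24 hours.* No section describes that series. It joins two conflicting schedules. Nor does any section name the 24-hour value as the main result.

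It is also fair to say that the missing group and group-by-time terms are the more basic fault, since a one-way analysis over time does not compare juice with placebo. That stands. Adding those terms to an ANOVA with a pooled within-man error would not remove the sphericity condition for time and group-by-time tests, so this point is not absorbed by that one.

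**Conclusion.** The concern holds in conditional form. Section 11 states neither a sphericity correction nor a contrast-specific error. If the ordinary pooled error is used, the validity of every time contrast rests on a condition unlikely to hold for all the listed markers. Distortion can go either way, and which contrast suffers depends on the marker.

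Under the assumed values the overstatement is the larger effect, at 1.7 to 2.3 times for the affected contrast. The understatement is 13% to 17%, and the F test runs at roughly 7% to 8% instead of 5%. Under mild or favourable assumptions (cases D and E) the effect is small or nil.

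The problem does not need a 24-hour sample, since case A arises from the Section 2 schedule alone. It merits a change of wording before analysis. It does not show that any particular result will be wrong.

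**What to change.** In Section 11, replace the pooled-error Tukey step with one of these:

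1. Juice versus placebo at each time, using that time's own variance: Welch's test, or ANCOVA on the baseline value. The D1 draw can serve as baseline if it is taken before the first product intake, which the protocol should state.
2. One mixed model with group, time, group-by-time and an unstructured covariance over times. If the named software cannot fit it, name software that can.

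Either option also supplies the missing between-group comparison. If a repeated-measures ANOVA of time changes is kept, specify the Greenhouse-Geisser correction for the F test, a separate error term for each contrast, and a multiplicity adjustment that does not rely on the pooled error.

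Before this, reconcile the blood schedules of Sections 2 and 8 with Section 10.3 so that the analysed times are defined. Section 1 describes four weeks of daily juice where Sections 2 and 9 describe 10 to 11 days. That must be reconciled too, because it sets the interval between the first and later draws.

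The cost is a few sentences, with no change in sample size or assessments. Error degrees of freedom fall: with 20 men and three times, from 19 × 2 = 38 pooled to 19 for a single paired contrast. The two-sided 5% t-value then rises from 2.02 to 2.09, about 3%, which is small beside the distortions above.
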